### **8.9.1 Immunogenicity assessments**

Blood samples for the measurement of ADAb and neutralizing antibodies will be collected. A total of 9mL will be collected at timepoints for which PK, ADAb, and neutralizing antibodies are all measured. Immunogenicity data will not be sent to the Investigator to protect the blinded nature of the treatment assignments and response.

Antibodies to bimekizumab will be evaluated in plasma samples collected from all participants according to the Schedule of Activities. Additionally, plasma samples should also be collected at the final visit from participants who discontinued IMP or were withdrawn from the study. These samples will be tested by the Sponsor or Sponsor's designee.

Plasma samples will be screened for antibodies binding to bimekizumab and the titer of confirmed positive samples will be reported. Other analyses may be performed to verify the stability of antibodies to bimekizumab and/or further characterize the immunogenicity of bimekizumab.

The detection and characterization of antibodies to bimekizumab will be performed using validated assay methods by or under the supervision of the Sponsor. All samples collected for detection of antibodies to bimekizumab will also be evaluated for bimekizumab plasma concentration to enable interpretation of the antibody data. Antibodies may be further characterized and/or evaluated for their ability to neutralize the activity of bimekizumab. Samples may be stored for a maximum of 20 years (or according to local regulations) following the last study participant's last visit for the study at a facility selected by the Sponsor to enable further analysis of immune responses to bimekizumab.

## **8.10 Medical resource utilization and health economics**

Health-related outcomes and medical resource utilization will be collected as part of standard eCRF pages during the study (eg, concurrent medical procedures, concomitant medications, hospitalizations, WPAI-SHP).

## **8.11 Photography**

At certain sites, where feasible, representative photographs of the changes in skin will be captured. Photographs will be anonymized. This is optional for study participants and requires a separate informed consent. A decision not to consent does not exclude the study participant from the study.

# **9 STATISTICAL CONSIDERATIONS**

A description of statistical methods follows and will be described in more detail in the Statistical Analysis Plan (SAP).

## **9.1 Definition of analysis sets**

### **9.1.1 Enrolled Set**

The Enrolled Set will consist of all study participants who have given informed consent.

### **9.1.2 Randomized Set**

The Randomized Set (RS) will consist of all randomized study participants.

### **9.1.3 Safety Set**

The Safety Set will consist of all study participants who received at least 1 full or partial dose of IMP and will be used for the demographic, safety, and immunogenicity analyses.

### **9.1.4 Full Analysis Set**

The Full Analysis Set (FAS) will consist of all study participants who received at least 1 dose (full or partial) of IMP and had a valid Baseline measurement and a post-Baseline measurement for abscess, inflammatory nodules, and draining tunnel counts.

### **9.1.5 Per-Protocol Set**

The Per-Protocol Set will consist of all study participants in the FAS who had no important protocol deviations affecting the primary efficacy variable. Important protocol deviations will be predefined and study participants with important protocol deviations will be evaluated during ongoing data cleaning meetings prior to unblinding of the data.

### **9.1.6 Pharmacokinetics Per-Protocol Set**

The Pharmacokinetics Per-Protocol Set will consist of study participants who received at least 1 full dose of bimekizumab and provided at least 1 quantifiable plasma concentration post-dose without important protocol deviations that would affect the PK. The Pharmacokinetics Per-Protocol Set is defined separately for each of the treatment periods (ie, separately for the Initial Treatment Period and the Maintenance Treatment Period).

### **9.1.7 COVID-19 Free Set**

The COVID-19 Free Set will consist of all study participants randomized into the study and who have no COVID-19 impact through Week 16. This analysis set will be used for sensitivity analysis of the primary efficacy endpoint.

## **9.2 General statistical considerations**

All analyses will be performed using SAS® version 9.4 or later (SAS Institute, Cary, NC, US).

Descriptive statistics will be used to provide an overview of the Baseline, efficacy, and safety results. For categorical parameters, the number and percentage of study participants in each category will be presented by treatment group. The denominator for the percentages will be based on the number of study participants appropriate for the purpose of analysis. Unless otherwise noted, all percentages will be expressed to 1 decimal place. For continuous parameters, descriptive statistics will include n, mean, standard deviation, median, minimum, and maximum. Two-sided 95% confidence intervals, geometric means, and coefficient of variation will be presented for selected variables as appropriate.

Baseline for each assessment is defined as either the value obtained at Baseline or the last available value obtained prior to treatment administration (details to be specified in the SAP).

Formal statistical testing will be conducted for this study for the primary and secondary efficacy variables. Other efficacy variables will be summarized descriptively by treatment arm. P-values and confidence intervals may be produced for other or exploratory variables but will be interpreted as non-inferential (ie, nominal). Additionally, other analyses will be conducted as deemed appropriate and described in the SAP.

The primary treatment comparison for all formal statistical analyses of efficacy will be between bimekizumab and placebo.

## **9.3 Planned efficacy/outcome analyses**

### **9.3.1 Analysis of the primary efficacy endpoint**

The primary objective of this randomized, double-blind, placebo-controlled, multicenter, pivotal study in study participants with moderate to severe HS is to compare the efficacy of bimekizumab 320mg Q2W and bimekizumab 320mg Q4W with placebo at Week 16. For the purposes of Week 16 analyses, the bimekizumab treatment arms of 320mg Q2W/Q2W and bimekizumab 320mg Q2W/Q4W treatment groups will be pooled.

The primary and secondary efficacy analyses will be performed based on the RS.

The primary endpoint is the HiSCR50 response at Week 16. The primary efficacy analysis will evaluate the composite estimand in the RS. The composite estimand combines the clinically meaningful improvement from Baseline based on the HiSCR50 response and early receipt of

systemic antibiotic rescue medication, or discontinuation of IMP due to an AE or lack of efficacy.

The following 4 attributes describe the estimand that will be used to define the treatment effect of interest for the primary efficacy analysis:

4. Population=Study participants meeting the protocol-specified inclusion/exclusion criteria.
5. Study participant-level outcome=HiSCR50 at Week 16.
6. Intercurrent event handling=An intercurrent event is defined as receipt of systemic antibiotic rescue medication or discontinuation of study treatment due to an AE or lack of efficacy prior to Week 16. A composite strategy will be implemented in which a positive clinical outcome is defined as achieving HiSCR50 at Week 16 and not receiving systemic antibiotic rescue medication, and not discontinuing study treatment due to an AE or lack of efficacy through Week 16. Any missing data at Week 16 that are not preceded by an intercurrent event will be imputed using multiple imputation.
7. Population-level summary measure=conditional odds ratio comparing bimekizumab to placebo adjusted for stratification factors used in the randomization.

As a sensitivity analysis, any missing data at Week 16 that are not preceded by an intercurrent event (ie, receipt of systemic antibiotic rescue medication, or discontinuation of IMP due to an AE or lack of efficacy) will be imputed as non-response.

The statistical hypothesis for the HiSCR50 response at Week 16 is that the conditional odds ratio for the HiSCR50 response in the bimekizumab treatment group relative to the placebo group is equal to 1.

A logistic regression model will be used to assess the effect of bimekizumab vs placebo on HiSCR50 response. The model will include a fixed effect for treatment. The stratification variables of Hurley stage and prior antibiotic use will be added to the model unless inappropriate. The odds ratio versus placebo, p-value (from Wald test), and confidence interval will be calculated.

To assess the impact of the COVID-19 pandemic on the primary efficacy endpoint analysis, additional sensitivity analyses will be performed as specified in Section 9.3.4.

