#### **6.5.3.2      Rescue Medications/Lesion Intervention**

There are no absolute restrictions on the use of rescue medications for study participants whose HS deteriorates during the study. While the objectives of the study should be protected as much as possible through observance of the restrictions detailed above in Section 6.5, the well-being of the study participant will always take priority; study participants should be managed as deemed appropriate by the Investigator.

In the event an acutely painful lesion occurs that requires an immediate intervention, Investigators will have the option to perform interventions. Interventions can include analgesics for a limited period of time (see below), intralesional injections of triamcinolone, and/or incision and drainage of the abscess. Intralesional injections of triamcinolone (up to 20mg across all lesions at a given visit, and using a concentration of no more than 20mg/mL [suspension for injection]) must be consistent with the maximum number of interventions described below and clinical practice. Concomitant use of wound care dressings is permitted; however, options are limited to alginates, hydrocolloids, and hydrogels. Concomitant medications associated with the lesion intervention(s) must be captured in source documents and on the appropriate eCRF.

Any analgesic that is initiated (new analgesic, new class of analgesic, increased dose of an analgesic stable since Baseline, regardless of duration of treatment) after Baseline (first day of study drug administration) will be considered rescue pain medication for the Initial Treatment Period and Maintenance Treatment Period (Weeks 0 to 48).

A total of 2 protocol-allowed interventions are permissible during the Initial Treatment Period (from Baseline Visit to Week 16). Do not include analgesic rescue treatment in the number of protocol-allowed interventions. An intervention can occur on maximally 2 different lesions at the same visit, or on the same lesion at 2 different study visits. The same lesion cannot be treated 2 times at the same visit. If a study participant requires more than 2 interventions within the first 16 weeks of the study, then the study participant should be discontinued from the study.

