## 7.2 Participant discontinuation/withdrawal from the study

Note: For female study participants, please see Section 8.3.5 for pregnancy that occurs during the study as evidenced by a positive pregnancy test.

Study participants are free to withdraw from the study at any time, without prejudice to their continued care.

A study participant may withdraw from the study at any time at his or her own request, or may be withdrawn at any time at the discretion of the Investigator for safety, behavioral, compliance, or administrative reasons.

If the study participant withdraws consent for disclosure of future information, the Sponsor may retain and continue to use any data collected before such a withdrawal of consent.

If a study participant withdraws from the study, he or she may request destruction of any samples taken and not tested, and the Investigator must document this in the site study records.

See the Schedule of Activities (Table 1-1) for data to be collected at the time of study discontinuation and follow-up and for any further evaluations that need to be completed.

If a study participant does not achieve a partial response (defined as a  $\geq 25\%$  reduction in AN count from Baseline [Week 0]) at any visit from Week 32 to 46, the Investigator should contact the Medical Monitor to discuss whether the study participant should continue on study.

Study participants will be withdrawn from the study, after being encouraged to complete the Premature End of Treatment (PEOT) and the SFU Visit if either of the following events occur:

1. Study participant withdraws his or her consent.
2. The Sponsor or a regulatory agency requests withdrawal of the study participant.

Study participants should be withdrawn from IMP and encouraged by the Investigator to return for all scheduled visits through Week 48, and the SFU Visit (if the Week 48 Visit is  $\geq 20$  weeks after the final dose of IMP, the SFU Visit is not required) if any of the following events occur:

1. Study participant develops an illness that would interfere with his or her continued participation.
2. Study participant is noncompliant with the study procedures or medications in the opinion of the Investigator.

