3. Study participant takes prohibited concomitant medications as defined in this protocol (Section 6.5.2) that may present a risk to the safety of the participant or the integrity of the study data, in the opinion of the Investigator and/or the Medical Monitor and/or UCB study physician.

4. Study participant requires more than the number of protocol-allowed lesion interventions (see Section 6.5.3.2).
5. Study participant has a clinical laboratory value meeting any of the following criteria:
  - a. Hepatotoxicity as described in Section 7.1.2.
  - b. A laboratory value meeting any of the following criteria:
    - Absolute neutrophil count  $<1.0 \times 10^3/\mu\text{L}$
    - Absolute lymphocyte count  $<200 \text{ cells}/\mu\text{L}$

Study participants may remain on IMP if the result is transient. A retest is required within 1 to 2 weeks at a scheduled or unscheduled visit. If the repeat absolute neutrophil count or absolute lymphocyte count is still below the allowable values, the participant must be discontinued from the IMP. If the repeat absolute neutrophil count or absolute lymphocyte count is above the allowable values, the participant may continue to receive IMP.

6. There is confirmation of a pregnancy during the study, as evidenced by a positive pregnancy test (see Section 8.3.5 for more information regarding pregnancies).
7. A study participant considered as having either a suspected new LTBI or who develops active TB or an NTM infection during the study (including but not limited to, conversion demonstrated by interferon gamma release assay [IGRA] or other diagnostic means) must be immediately discontinued from IMP.
  - The study participant must immediately be permanently withdrawn from the study if further examinations result in a diagnosis of the following:
    - active TB or
    - an NTM infection, or
    - latent TB infection and study participant does not initiate TB prophylactic therapy, prematurely discontinues TB prophylactic therapy, or, in the opinion of the Investigator or Sponsor, is noncompliant with TB prophylactic therapy.

The PEOT Visit must be scheduled as soon as possible, but not later than the next regular visit.

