3. The treatment policy strategy for addressing intercurrent events will be considered. This will be based on an analysis of all available data at Week 16 regardless of the occurrence of intercurrent events. This analysis will use the same models specified for the primary analysis, where study participants are analyzed according to their randomized treatment, even if they discontinued study treatment for any reason prior to Week 16. Even though efforts will be made to collect the primary outcome data for all study participants at Week 16, there may still be some study participants for whom Week 16 efficacy data cannot be obtained. In this case, missing data will be imputed using multiple imputation under the assumption of MAR. Results will be combined into a single inference using Rubin's rule. It should be noted that this measures something different from the primary analysis and could be confounded by placebo study participants who withdraw and are subsequently on another active medication at the time of the Week 16 assessment. Therefore, the results of this analysis should be interpreted in the appropriate context.
4. An additional supportive analysis will be based on observed data only for study participants who are still on the randomized treatment at Week 16. Study participants with missing data or who have prematurely discontinued study treatment will be treated as missing. The same procedure described as in the primary efficacy analyses will be used.

All imputation of other missing data will be detailed in the SAP.

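### The primary estimand counts new antibiotics as failure but not the start of another prohibited systemic HS therapy, so a Week 16 response on that therapy is credited to the randomised arm

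*Protocol*

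**What the plan says.** **The event list.** Protocol Section 9.3.1 names two kinds of intercurrent event: systemic antibiotic rescue, and "discontinuation of study treatment due to an AE or lack of efficacy prior to Week 16". A positive outcome is HiSCR50 at Week 16 together with "not receiving systemic antibiotic rescue medication, and not discontinuing study treatment due to an AE or lack of efficacy through Week 16".

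**Missing data.** The same section says: "Any missing data at Week 16 that are not preceded by an intercurrent event will be imputed using multiple imputation". No rule there sets an observed Week 16 value to missing or to non-response because of other therapy.

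**Stopping study drug.** Section 7.2 gives its own list of reasons for withdrawing IMP. One is: "Study participant takes prohibited concomitant medications as defined in this protocol", where this is judged a risk to safety or data integrity. Participants withdrawn for these reasons are to be "encouraged by the Investigator to return for all scheduled visits through Week 48".

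**Rescue.** Section 6.5.2 prohibits biologics and systemic steroids, among others. Section 6.5.3.2 states: "There are no absolute restrictions on the use of rescue medications for study participants whose HS deteriorates during the study". It goes on to ask that the Section 6.5 restrictions be respected as far as possible.

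**The protocol's own caution.** Section 9.6, item 3 says that the supportive treatment-policy analysis "could be confounded by placebo study participants who withdraw and are subsequently on another active medication at the time of the Week 16 assessment".

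**The concern.** The primary question is the effect of bimekizumab over placebo at Week 16. The composite treats a newly started systemic antibiotic as failure of the randomised treatment. It does not treat a newly started biologic that way, although the protocol prohibits such drugs because they may affect HS.

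Two routes lead to an observed response on another drug:

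- The participant starts a prohibited systemic therapy, is withdrawn from IMP with that recorded as the reason, keeps attending and meets HiSCR50 at Week 16.
- The participant starts such therapy but stays on IMP, because withdrawal under that item depends on a judgement of risk.

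Neither is an intercurrent event. Had the first participant's stop been recorded as lack of efficacy, the same Week 16 count would be non-response, so the outcome turns on how the site labels the stop. HiSCR75 and pain response are to be analysed similarly to the primary (Section 9.3.2) and inherit the gap.

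**Working it through.** **1. Is such a case caught anywhere in the primary analysis?**

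| Situation before Week 16 | Event in 9.3.1? | Week 16 value used |
|---|---|---|
| New systemic antibiotic | Yes | Non-response |
| IMP stopped, recorded as AE or lack of efficacy | Yes | Non-response |
| Prohibited systemic HS therapy, IMP stopped for another recorded reason, Week 16 attended | No | As observed |
| Prohibited systemic HS therapy, IMP continued | No | As observed |
| IMP stopped for another reason, Week 16 missing | No | Multiple imputation |

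Rows three and four are the gap. The non-response sensitivity analysis in 9.3.1 and the reference-based and tipping-point analyses in 9.6 address missing data. These data are observed.

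**2. Reproduce the stated power.** Inputs from Table 9-1 and Section 9.8: HiSCR50 rate 0.25 on placebo (n = 70), 0.50 on Q4W (n = 140), 0.60 on pooled Q2W (n = 280); two-sided alpha 0.025, so z = 2.241.

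Power = Φ[(|p2 − p1| − z·SE0)/SE1], with SE0 = √[p̄(1 − p̄)(1/n1 + 1/n2)] and SE1 = √[p1(1 − p1)/n1 + p2(1 − p2)/n2].

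Q4W: p̄ = (70 × 0.25 + 140 × 0.50)/210 = 0.4167; SE0 = 0.0722; SE1 = 0.0668. Power = Φ[(0.25 − 2.241 × 0.0722)/0.0668] = 0.907 (stated 0.90). Q2W: 0.9996 (stated 0.99). Both agree.

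**3. Effect of the rule as written.** The protocol gives no switching rate. Assume that a share x of placebo participants switch by one of the two routes, are observed at Week 16, and respond at 50%. Then placebo response = 0.25(1 − x) + 0.50x. The odds ratio is crude, Q4W against placebo.

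| x | Placebo response | Odds ratio | Q4W power | Q2W power |
|---|---|---|---|---|
| 0 | 0.250 | 3.00 | 0.907 | 0.9996 |
| 2% | 0.255 | 2.92 | 0.892 | 0.9995 |
| 5% | 0.2625 | 2.81 | 0.869 | 0.999 |
| 10% | 0.275 | 2.64 | 0.822 | 0.998 |

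At 60% response among switchers, Q4W power is 0.886, 0.851 and 0.779 for the three shares, and Q2W power stays at or above 0.996.

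**4. Compare with the fix, not with no switching.** If the same share switches in the Q4W and placebo arms with 50% response, Q4W response as written stays at 0.50(1 − x) + 0.50x = 0.50, so as-written power is as in step 3. Under the fix the rates are 0.50(1 − x) and 0.25(1 − x).

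| x | As written | Fix, equal switching | Gain (points) |
|---|---|---|---|
| 2% | 0.892 | 0.896 | 0.4 |
| 5% | 0.869 | 0.878 | 0.9 |
| 10% | 0.822 | 0.845 | 2.3 |

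If switching occurs on placebo only, the fix gives placebo rates of 0.245, 0.2375 and 0.225, and Q4W power of 0.920, 0.937 and 0.959.

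**The case against.** **Most such cases should already be caught.** A participant who deteriorates and needs another systemic drug has, in substance, stopped for lack of efficacy, and the eCRF must record the primary reason. Any new or changed systemic antibiotic is caught too. This stands, and it limits the numbers. It does not close the gap, because Section 7.2 makes prohibited medication a separate reason and because therapy taken while on IMP is no event at all.

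**The rescue sentence is not an invitation to switch.** In context, Section 6.5.3.2 protects participant welfare, asks for the restrictions to be observed, and then names analgesics, intralesional triamcinolone, and incision and drainage. A reader might infer that switching to a biologic is a planned pathway; the text does not support that. It shows only that such use can occur.

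**Supportive checks exist.** Section 9.6, item 4 uses only participants still on randomised treatment at Week 16, and the Per-Protocol Set excludes important deviations affecting the primary variable. Both would help show whether the issue matters. But item 4 retains those who take other therapy while on IMP, and neither analysis is primary.

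**Section 9.6 does not say that the primary is free of this confounding.** True. It says that the treatment-policy analysis measures something different and attaches the caution there. The remaining point is narrower: the same observed data enter the primary, and the caution is not carried over.

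**Placebo participants have a reason to stay**, since they receive bimekizumab from Week 16. This also argues for small numbers.

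**It is late.** Section 9.8 says that pain response was added after randomisation was complete. It came in with Amendment 4 (09 May 2022); Amendment 5 is dated 27 September 2022, 141 days or about 20 weeks later. All Week 16 visits were therefore due before the current version. This bears on how the fix is made, not on whether the gap exists.

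**Conclusion.** The gap is real. As Section 9.3.1 is worded, an observed Week 16 HiSCR on another prohibited systemic HS therapy is credited to the randomised arm unless the stop is recorded as AE or lack of efficacy, or a systemic antibiotic was also started.

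Two stronger readings are not supported. A reader might infer a threat to the type I error rate: if switching is mainly on placebo, the bias is toward no effect and does not by itself inflate that error. The same rule in a bimekizumab arm could add responses that are not due to bimekizumab, but nothing in the protocol suggests that this would dominate. A reader might also infer a material loss of power. The 2% to 10% range and the 50% response are assumptions, and the true number may be close to none. Even at 10%, Q2W is hardly affected, and with equal switching the fix recovers only 0.4 to 2.3 points for Q4W.

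The case for change is therefore validity: like events should be handled alike, and the primary result should not depend on the stopping reason recorded.

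**What to change.** Add to the intercurrent events in Section 9.3.1, and so for HiSCR75 and pain response, the start before Week 16 of a prohibited systemic therapy with potential therapeutic effect on HS. Apply it whatever the recorded reason for stopping IMP, and whether or not IMP was stopped, and handle it as non-response under the existing composite strategy.

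Identify cases by blinded review of the concomitant-medication eCRF before unblinding. Exclude short courses for unrelated conditions that the blinded review judges not to affect HS, for example a systemic steroid given for something else.

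Reconcile the caution in Section 9.6, item 3 with the primary definition: either state that it applies to the primary as now worded, or confine it to the treatment-policy analysis once the clause is added.

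If the primary estimand cannot be changed at this stage, keep it and prespecify the same rule as a sensitivity analysis before unblinding.

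Cost: one clause and a blinded adjudication of medications already collected. A few participants in each arm become non-responders. Conduct and clinical management are untouched.
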